4.5. Concomitant therapies

Concomitant therapies will be listed per treatment arm. Both the medication and the indication will be listed. Concomitant therapies administered nasally and anti-virals used will also be summarised.

5. ANALYSIS OF THE PRIMARY OUTCOME(S)

5.1. Main analysis

The primary outcome will be the number (and proportion) of household members swab negative on day 1 (study timepoint called baseline) testing positive for SARS-CoV-2 by PCR on either of three routine nasopharyngeal swabs on day 3, 5 and 10 after enrolment.

Primary estimand

Population: Household members (including children < 5 years) who test negative for SARS CoV-2 on day 1 (baseline) PCR testing using the health care provider swabs

Treatment: Initially randomised intervention to unfractionated intranasal heparin 1400u each nostril (as heparin solution 5,000u/ml, 140microL/actuation, TWO actuations each nostril) THREE times daily via a plastic nasal inhalator device or saline control and any subsequent deviations to the per protocol use of the intervention over 10 days

Outcome: Testing positive for SARS-CoV-2 by PCR on any of three health care provider collected swabs at days 3, 5 and 10. The algorithm to determine SARS-CoV-2 positivity is described in detail in Section 3.8. If one of the post-baseline swabs is missing, but all observed swabs were negative, the participant will be regarded to be negative. If more than one post-baseline swab is missing and the observed swabs were all negative, the outcome will be regarded to be missing.

Summary measure: Both relative (risk ratio) and absolute differences (risk difference) in proportions will be reported with 95% confidence intervals

Potential intercurrent events:

Index case in the household not taking study drug. This is defined as compliance <90% Participant (this household member) not taking study drug. This is defined as compliance <90% Either participant (this household member) or index case stop treatment due to adverse event Participant hospitalisation during first 10 days (removed from household) Participant received an anti-viral

Strategy for handling intercurrent event:

In the primary analysis all intercurrent events will be handled through the treatment policy strategy, which means that the intercurrent events will be ignored.

The analysis will follow the intention to treat principle, but only some households will be eligible for this objective. A household will be eligible if there is at least one participant in the household who tested positive to SARS-CoV-2 by PCR on Day 1 and one participant who tested negative to SARS-CoV-2 by PCR on Day 1, using the health care provider collected swab. It does not matter whether it was the index case or another household member who tested positive. Households where all participants test positive or where all participants test negative will not be eligible for this analysis.

Treatment arms will be compared using generalised linear mixed models (GLM) with infection status as the binary outcome, adjusting for stratification factors (time from positive test to randomisation, whether the index case is a child < 5 years), participant age, inhaled steroid use at baseline, days since symptom onset at randomisation, whether there are children in the household and household size (referred to as the defined baseline covariate set, see Section 3.9), with household as random effect to take the clustering by household into account. Both relative and absolute differences in proportions will be reported with 95% confidence intervals.

Relative differences (risk ratios) between the treatment arms will be calculated using a Poisson regression with robust standard errors in Stata as follows:

xtpoisson outcome i.arm baseline_covariates, re vce(robust) irr

Absolute differences (risk difference) between the treatment arms will be calculated in Stata as follows using a mixed effects GLM with random intercepts: megIm outcome i.arm baseline_covariates || household:, family(bin) link(logit)

The margins statement will be used to compute the risk difference by subtracting the probability of the outcome in the control arm from the probability in the treatment arm margins i.arm, atmeans post lincom _b[1.arm] - _b[0.arm]

Both these models are fairly complicated models to fit and might not converge if sparse data is encountered, given all the baseline covariates included. If the models do not converge, the following strategies will be tried:

- Exclude some of the baseline covariates especially binary covariates, covariates with sparse categories, or covariates with little variability
- Or, fit the following simpler models

Relative differences (risk ratios) between the treatment arms will be calculated in Stata as follows using robust standard errors:

glm outcome i.arm baseline_covariates, fam(bin) link(log) nolog eform vce(cluster household)

Absolute differences (risk difference) between the treatment arms will be calculated in Stata as follows using robust standard errors:

glm outcome i.arm baseline_covariates, fam(bin) link(identity) nolog vce(cluster household)

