UFH	Unfractionated Heparin
WAIS	Wechsler Adult Intelligence Scale

Clarification of terms used:

Day 1 swab: Day 1 swab is defined as the swab taken before starting study drug. This could be on the same day as starting study drug.

Index case: The initial SARS-CoV-2 infected person who reached out for enrolment into the study. In the analysis, the index case is not analysed separately from the other household members. The index case does play a role in the randomisation by determining one of the randomisation strata. Some of the covariates included in multivariate models are also determined at the index case level.

Household contact: A household contact is any household member other than the index case.

Household member: This is a synonym for study participant, and means index cases and household contacts combined. For most analyses, we will include household members, by their SARS-CoV-2 status on day 1.

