2.1. Primary objective

To test the efficacy of early treatment and post exposure prophylaxis to reduce transmission to household family contacts on SARS-CoV-2 PCR assay by day 10.

Measure: Number of household contacts (swab negative on day 1) testing positive for SARS-CoV-2 by PCR on either of three routine nasopharyngeal swabs on day 3, 5 and 10 after enrolment or on clinically driven swab in the first 10 days. Day 1 swab is defined as the swab taken before starting study drug. This could be on the same day as starting study drug.

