5.3. Supplementary analyses

We define a supplementary estimand, through handing the intercurrent event of not taking study drug differently.

Supplementary estimand

Population: Household contacts who test negative for SARS CoV-2 on day 1 (baseline) PCR testing using the health care provider swabs

Treatment: Unfractionated intranasal heparin 1400u each nostril (as heparin solution 5,000u/ml, 140microL/actuation, TWO actuations each nostril) THREE times daily via a plastic nasal inhalator device or saline control

Outcome: Testing positive for SARS-CoV-2 by PCR on any of three health care provider collected swabs at days 3, 5 and 10 while participant and index case do not discontinue treatment due to adverse events. The algorithm to determine SARS-CoV-2 positivity is described in detail in Section 3.8. If one of the post-baseline swabs is missing, but all observed swabs were negative, the participant will be regarded to be negative. If more than one post-baseline swab is missing and the observed swabs were all negative, the outcome will be regarded to be missing.

Summary measure: Both relative (risk ratio) and absolute differences (risk difference) in proportions will be reported with 95% confidence intervals

Potential intercurrent events:

Index case in the household not taking study drug. This is defined as compliance <90% Participant (this household member) not taking study drug. This is defined as compliance <90% Either participant (this household member) or index case stop treatment due to adverse event Participant hospitalisation during first 10 days (removed from household) Participant received an anti-viral

Strategy for handling intercurrent event:

Index case in the household not taking study drug. This is defined as compliance <90%: This intercurrent event will be handled following the hypothetical strategy. For index cases who used <90% of study drugs we will set all SARS-CoV2 infections observed in the household to missing. We will use multiple imputation to impute these outcomes.

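### The primary estimand admits day 1 PCR-negative index cases to the at-risk set, although the primary objective, the sample size and the supplementary estimand are set in household contacts

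*SAP*

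**What the plan says.** The SAP's clarification of terms separates three groups. The index case is "The initial SARS-CoV-2 infected person who reached out for enrolment into the study". For contacts, "A household contact is any household member other than the index case". Of household member it says: "This is a synonym for study participant, and means index cases and household contacts combined".

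The primary question is then set in two different groups:

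- **Contacts.** The measure in Section 2.1 is the "Number of household contacts (swab negative on day 1) testing positive for SARS-CoV-2 by PCR". Section 2.6 sizes the trial on 360 household contacts per arm. Section 5.3 gives the supplementary estimand as "Population: Household contacts who test negative for SARS CoV-2 on day 1 (baseline) PCR testing using the health care provider swabs". The other two outcomes in people negative on day 1, measures 3.1 and 4.2 (Sections 6.3 and 6.4), are also set in contacts.
- **Members.** The primary estimand in Section 5.1 is set in "Household members (including children < 5 years) who test negative for SARS CoV-2 on day 1 (baseline) PCR testing", and the second population in Section 3.4 matches it.

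Section 5.1 makes a household eligible if it has at least one PCR-positive and one PCR-negative participant on day 1, and adds: "It does not matter whether it was the index case or another household member who tested positive". Section 2.3 lets an index case enter on a RAT or a laboratory PCR no more than 72 hours old. A RAT entrant then has a confirmatory PCR before study drug, which is the day 1 swab.

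**The concern.** Put together, these rules allow the following. An index case tests positive, enrols within 72 hours, and has a negative day 1 PCR. Someone else in the house is PCR positive on day 1, so the household qualifies. The index case enters the primary denominator as uninfected, and a detected result on day 3, 5 or 10 counts as a primary event. If the entry test was right, that event need not be transmission within the household. It may be the original infection, missed by one swab or shed intermittently.

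Two things are at stake. Such people can dilute a true effect on contacts. And secondary objective 1 asks whether heparin reduces shedding: if it does, fewer repeat positives in index cases would appear in the primary result as fewer transmissions.

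There is also an internal inconsistency. Section 5.3 presents the supplementary estimand as differing in how non-use of study drug is handled, yet its population differs too. Table 8 shows both estimands together, so a gap between them would mix strategy with population.

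**Working it through.** **1. Which population does the sample size assume?** Inputs from Section 2.6: 85% against 75%, ICC 0.2, two-sided alpha 0.05, 80% power, 3 additional members per household.

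- Two proportions, pooled variance under the null: n = [1.96·√(2·0.80·0.20) + 0.842·√(0.85·0.15 + 0.75·0.25)]² / 0.10² = 250 per arm.
- Contacts only, 3 per household: design effect 1 + (3−1)·0.2 = 1.4; 250·1.4 = 350 contacts; 350/3 gives 117 households per arm. The SAP states 120, which is within 3%. Its 360 contacts give 81.1% power.
- Loss to follow-up: 120/0.9 gives 134 per arm; 2·134·4 = 1072 people, as stated.
- Two contacts: design effect 1.2; 250·1.2/2 = 150; 150/0.9 gives 167 per arm; 334 households and 1002 people, as stated.
- Index case also at risk, 4 per household: design effect 1.6; 250·1.6/4 = 100 households per arm. This does not reproduce 120.

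The sample size was built on contacts only.

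**2. Share of index cases in the primary set.** The SAP gives none of the inputs, so these are assumptions. Let q be the share of eligible households whose index case is PCR negative on day 1, and m the mean number of day 1-negative contacts per eligible household. The index share is f = q/(q + m). If index cases show no arm difference, the planned 10 points become 10·(1 − f).

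| q | m | f | Diluted difference |
|---|---|---|---|
| 5% | 3 | 0.05/3.05 = 1.6% | 9.8 points |
| 5% | 1 | 0.05/1.05 = 4.8% | 9.5 points |
| 15% | 3 | 0.15/3.15 = 4.8% | 9.5 points |
| 15% | 1 | 0.15/1.15 = 13.0% | 8.7 points |

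**3. Power.** Take the planned 120 households and 360 contacts per arm, and let later positivity in the added index cases be the same in both arms, at 20–90% (assumed). The contacts-only reference is 81.1%.

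| Index cases PCR negative | Added per arm | Share of set | Difference | Power |
|---|---|---|---|---|
| 5% | 6 | 6/366 = 1.6% | 9.8 points | 79–80% |
| 10% | 12 | 12/372 = 3.2% | 9.7 points | 77–80% |
| 20% | 24 | 24/384 = 6.2% | 9.4 points | 72–78% |

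**4. The opposite direction, as an illustration.** Suppose no effect in contacts (80% in both arms) and repeat positivity in index cases of 60% on placebo and 30% on heparin. The apparent difference is f·(60 − 30): 0.5 points at f = 1.6%, 1.4 points at 4.8%, and 3.9 points at 13%. All of these rates are invented, and the last figure combines the extreme assumptions.

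**The case against.** The strongest reply is that the pooling looks intended. The clarification of terms says that the index case is not analysed separately and that most analyses classify members by day 1 status. Section 2.3 ties the primary outcome to a negative day 1 PCR, and the eligibility rule in Section 5.1 is explicit. The rule is also fair between arms, since it uses a swab taken before treatment in both. If heparin affects neither infection nor shedding, these index cases create no expected difference.

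That stands, as does a further point. Entry can rest on a RAT alone, so an index case with a positive RAT and a negative PCR may be a false positive who is susceptible and lives with a PCR-positive person. A reader might infer that no such person can tell us anything about transmission; the SAP does not support that.

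Two other inferences go too far. One is that every day 1-negative index case is counted: Section 5.1 removes households in which everyone is negative. The other is that Section 2.8 conceals a change: that section lists departures from the protocol, and whether this is one cannot be judged from the SAP.

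None of this reconciles Section 5.1 with Sections 2.1, 2.6 and 5.3, and the SAP gives no reason for using a wider group than its objective names.

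**Conclusion.** The primary estimand does not match the primary objective, and it differs in population from the supplementary estimand reported beside it. That follows from the SAP's own definitions and needs no assumption.

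The numerical consequence does rest on assumptions and is probably small: index cases at about 1.6–13% of the primary set, and a 10-point difference reduced to about 9.8–8.7 points if they show no arm difference. With three day 1-negative contacts per household, as in the sample size, the same range of q gives 9.8–9.5 points. A shedding effect read as a transmission effect is possible, but it requires heparin to act on shedding in these index cases. A reader might conclude that the primary result would be seriously biased; the SAP contains no figure that shows this. The case for correction is one of definition: who is counted should not depend on which section the analyst follows.

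**What to change.** In Section 5.1, set the primary outcome and the estimand population to household contacts, including children under 5, who are PCR negative on day 1. Make the same change in the second population of Section 3.4. Keep the rule that a household needs at least one PCR-positive member on day 1, whoever that is. Report the all-members version as a sensitivity analysis. Measure 1.6 is also written for day 1-negative household members, so its wording should be checked at the same time.

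The cost is a slightly smaller primary set. PCR-negative index cases also fall outside measures 1.1–1.5, 3.1 and 4.2, so the sensitivity analysis is needed to keep their swab results reported. The sample size needs no change, because it already counts contacts only. The restriction does not deal with contacts whose own day 1 swab was falsely negative; that limitation remains under either population.

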2.6 Sample size

For the primary research outcome, a sample size of 120 index cases per arm will provide 80% power. We anticipate that the attack rate for within household transmission will be approximately 85% in the control arm and 75% in the intervention arm. Under these assumptions, in a cluster randomised trial with a binary outcome, assuming an intracluster correlation coefficient of 0.2, an alpha of 0.05 (two sided), and assuming 3 additional household members (in addition to the index case) we have 80% power to detect a reduction in transmission to household contacts. The requisite sample size is then 120 index cases and 360 household contacts per arm. Allowing for 10% loss to follow-up this is increased to 134 index cases (households) per arm, approximately 536 persons per arm. We plan to enroll 268 households and approximately 1072 individuals.

If the household size is 2 additional people, rather than 3, and with all other assumptions the same, we would require 334 households and approximately 1002 individuals. The target sample size for the primary outcome is 1100 individuals enrolled.

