3.7. Handling of missing data

If less than 10% of data is missing, the primary analysis will be conducted using the participants with available data for each outcome. However, if there are >10% missing data in the primary or secondary outcomes, we will conduct the analysis under a plausible assumption regarding the missingness mechanism that will be guided using expert clinical knowledge prior to observing the data, which will be determined by generating directed acyclic graphs. We suspect that the data will be recoverable (that is able to be estimated without bias from the observed data alone), and multiple imputation will be used to handle the missing data in all

outcomes. Imputations will be generated using chained equations, also known as fully conditional specification, with 50 imputed datasets and 10 iterations between each imputation. Ideally this would be conducted using a single regression model for all outcomes, although it may be necessary to impute incomplete outcomes using separate models. Imputation will be carried out separately by arm, to ensure that any treatment effects are maintained. Baseline characteristics as well as any variables that are predictors of missingness and/or associated with the incomplete outcomes will be included as auxiliary variables in the imputation model. Estimates of interest will be obtained using Rubin's rules, and will be reported with 95% confidence intervals and *p*-values.

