5.2. Sensitivity analyses

Four sensitivity analyses are planned:

- 1. The analysis described above will be repeated using multiple imputation, if more than 10% of outcome data is missing.
- 2. The analysis described above willbe repeated without the covariates participant age, inhaled steroid use at baseline, days since symptom onset at randomisation, whether there are children in the household and household size.
- 3. The algorithm to determine SARS-CoV-2 infection will be changed by deeming all inconclusive results (including on Day 0) to be positive, using only healthcare provider collected swabs.
- 4. The algorithm to determine SARS-CoV-2 infection will be changed by deeming all inconclusive results (including on Day 0) to be negative, using only healthcare provider collected swabs.

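### The primary outcome's missing-swab rules select on the result, so both arm risks are biased even when swabs are missed completely at random; the net shift in the risk difference is small unless missingness is heavy or differs by arm

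*SAP*

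**What the plan says.** SAP Section 5.1 defines the primary outcome as "Testing positive for SARS-CoV-2 by PCR on any of three health care provider collected swabs at days 3, 5 and 10". Two rules cover missing swabs:

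- One missing: "If one of the post-baseline swabs is missing, but all observed swabs were negative, the participant will be regarded to be negative".
- Two or three missing: "If more than one post-baseline swab is missing and the observed swabs were all negative, the outcome will be regarded to be missing".

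No rule sets an observed positive to missing. Section 5.3 repeats both rules for the supplementary estimand.

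On missing outcomes, Section 3.7 states: "If less than 10% of data is missing, the primary analysis will be conducted using the participants with available data for each outcome". Above that level it turns to multiple imputation by chained equations, separately by arm. Section 5.2 lists the primary analysis "repeated using multiple imputation, if more than 10% of outcome data is missing" as a sensitivity analysis. The other three sensitivity analyses drop covariates or reclassify inconclusive swabs. None changes either missing-swab rule.

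**The concern.** Among participants with two swabs missing, the observed result decides who is analysed: one positive keeps the person and one negative removes them. Everyone kept from that group is a case, whatever the true risk. An available-case analysis therefore overstates risk in that group even if swabs are missed completely at random.

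The one-missing rule errs the other way. A missed day 10 swab leaves days 5 to 10 unobserved, yet it is treated like a missed day 3 swab followed by two negatives. Infections that would have shown only at the missed swab become negatives.

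Those negatives are recorded as observed data. They are never imputed, they do not count towards the 10% threshold, and they would enter any imputation model as true zeros. The primary risk ratio and risk difference rest on this coding.

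**Working it through.** **The plan's own figure.** Inputs from SAP Section 2.6: "We anticipate that the attack rate for within household transmission will be approximately 85% in the control arm and 75% in the intervention arm"; "assuming an intracluster correlation coefficient of 0.2, an alpha of 0.05 (two sided"); "assuming 3 additional household members (in addition to the index case"); 80% power.

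- Per arm without clustering: [1.96√(2×0.8×0.2) + 0.8416√(0.85×0.15 + 0.75×0.25)]² / 0.10² = 250.
- Design effect 1 + (3−1)×0.2 = 1.4, so 350 contacts or 117 households per arm. The SAP has 120, which gives 81.1% power.
- 120/0.9 rounds up to 134, as stated.

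The sample size reproduces and is not in question. It also gives a yardstick: with 360 contacts per arm, SE(RD) = √(0.315×1.4/360) = 0.035, a 95% half-width of 6.9 points.

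**Assumptions.** The SAP gives neither swab-level missingness nor the timing of positivity, so both are varied. Let a, b and c be the shares of infections that would be positive on one, two or three of the swabs:

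- Pattern A: first positive on day 3/5/10 in 50/30/20%, then staying positive (a, b, c = 0.2, 0.3, 0.5).
- Pattern B: the same with 30/30/40% (0.4, 0.3, 0.3).
- Pattern C: transient shedding (0.4, 0.6, 0).

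**Each rule alone, swabs missing at random.**

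- Exactly one missing: observed risk = p(1 − a/3). For p = 0.85 this is 0.793 (A) or 0.737 (B, C); for p = 0.75 it is 0.700 or 0.650.
- Exactly two missing: share kept = p(a + 2b + 3c)/3, and all of those kept are positive. For p = 0.85 under A, 0.85×2.3/3 = 0.652 are kept and 34.8% dropped. Over both planned risks and all patterns, 35–60% are dropped, and the observed risk is 100%.

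**Both rules together, each swab missing independently with probability q.**

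- Positive = p[a(1−q) + b(1−q²) + c(1−q³)]
- Infected but coded negative = p·a·q(1−q)²
- Uninfected and kept = (1−p)[1 − 3q²(1−q) − q³]
- Observed risk = positive / sum of the three

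Example, pattern A, q = 10%:

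- Control: 0.8300/(0.8300 + 0.0138 + 0.1458) = 0.8388.
- Heparin: 0.7324/(0.7324 + 0.0122 + 0.2430) = 0.7416.
- RD = −9.7 points.

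Equal missingness in both arms, range over A to C:

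| Missing per swab | Control risk | Heparin risk | RD (points) | Outcome missing |
|---|---|---|---|---|
| 5% | 0.835–0.843 | 0.737–0.744 | −9.8 to −9.9 | 0.3–0.4% |
| 10% | 0.824–0.839 | 0.728–0.742 | −9.6 to −9.7 | 1.0–1.7% |
| 20% | 0.811–0.837 | 0.719–0.744 | −9.1 to −9.3 | 4–7% |
| 30% | 0.807–0.843 | 0.721–0.756 | −8.6 to −8.7 | 9–14% |

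Monotone dropout of 5–30% gives RD −9.3 to −9.9.

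**The trigger.** At 20% missing per swab, 1 − 0.8³ = 49% of participants lack at least one swab, but only 4–7% have a missing outcome. Imputation is not reached.

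**No true effect (risk 0.80 in both arms).** Equal missingness gives RD 0. With unequal missingness (control v heparin):

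- 5% v 20% per swab: −0.3, −1.9 and −2.1 points under A, B and C. For C, the observed risks are 0.7861 and 0.7650.
- 10% v 30% per swab: +0.9, −0.8 and −1.2.
- 10% v 30% dropout: −0.7, −2.3 and −0.7. The −2.3 (RR 0.970) is the largest seen.

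**The case against.** The strongest defence is that the asymmetry belongs to the endpoint. One positive settles an any-positive outcome; one negative does not. Calling the first known and the second missing is accurate, and the fix below also imputes only people with no observed positive. That is right, but it does not rescue the analysis: dropping the unsettled group is what biases an available-case comparison, and filling it in does not. Nor does it cover the one-missing rule, which calls an unsettled outcome known.

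The second defence is size, and it stands. At 10% missing per swab, equal by arm, the largest shift is 0.43 points, or 0.43/3.5 = 0.12 of a standard error. Large effects need heavy or arm-dependent missingness. The SAP reports neither; the trial is double-blind, and these swabs are taken by health care providers. Adverse-event withdrawal and hospitalisation, both listed as intercurrent events, could affect swab attendance, but the SAP gives no rate.

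Three stronger readings are tempting, and the SAP does not support them.

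- That the primary risks are biased upward overall. This is true of the two-missing rule only; with both rules acting, the risks are mostly too low.
- That one rule's effect can be quoted alone. The rules oppose each other. Moreover, if 20% of participants had two swabs missing, and 50% (control) and 40% (heparin) of those were already positive, 0.2×0.5 = 10% and 0.2×0.6 = 12% of outcomes would be dropped. That is 11% pooled, so the planned imputation would start.
- That imputing the composite cannot help, because everyone dropped has an early negative swab. Some have no swab at all and some have only day 10. Section 3.7 admits auxiliary variables associated with the outcome, and observed swabs qualify. Composite imputation could therefore help the dropped group; it never reaches negatives with one swab missing.

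**Conclusion.** The point holds as a defect of coding and of sensitivity analysis. Under the stated rules the arm risks are biased even when swabs are missed completely at random, through two mechanisms that partly cancel. At the planned risks the net result is a mild attenuation of the risk difference: 0.1 to 0.4 points with 5–10% of each swab missing equally by arm, and 0.7 to 0.9 points at 20%. Under no effect there is no bias unless missingness differs by arm. It then reaches about 2 points in the settings tried, roughly 0.6 of a standard error (2.1/3.5), in a direction that depends on timing and pattern.

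A reader might infer that the primary comparison will be materially wrong. That does not follow. The missingness rates and positivity timings are assumptions, and with light, balanced missingness the effect is minor. The case for changing the rule is that the SAP has no analysis that would reveal the problem if missingness proved heavy or unbalanced, and that the 10% trigger cannot see people with one missing swab. The change is worth making but is not critical.

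**What to change.** In Sections 5.1 and 5.3:

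- Impute the day 3, day 5 and day 10 results separately, conditional on the observed swabs, for every participant with a missing swab and no observed positive. Fit the model to all participants' swab data, including those with an observed positive.
- Derive the any-positive outcome from the completed swabs.
- Run this whether or not the 10% trigger is met, and keep the current coding as the comparison analysis.
- If the swab-level model does not converge, report at least a prespecified sensitivity analysis with best-case and worst-case bounds for participants with one or more missing swabs.
- Tabulate missing swabs by day and arm, so that readers can judge which row of the range above applies.

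Cost: SAP wording and a little more programming within the chained-equations method already planned. The real risk is sparse cells: three serially dependent binary results, imputed by arm in clustered data, may not converge. The SAP already warns of convergence problems in its outcome models, which is why the fallback bounds should be fixed in advance.
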